Nature and extent of the burden and risks associated with participation, benefit and group relatedness: In addition to the benefits from regular care, the primary hip arthroplasty procedure, patients might benefit from randomization to receiving a DM cup. DM cups are designed to reduce the risk of hip dislocation, compared to a unipolar cup. Patients may undergo more thorough follow-up than non-study patients and may benefit from this increased surveillance compared with regular care. The only burden associated with study

participation is the time needed to complete the cost questionnaires (all other outcomes are part of standard care).

INTRODUCTION AND RATIONALE

Dislocation is the leading reason for early revision surgery. In the Netherlands, 34.5% of all revisions within the first year after surgery, performed between 2010 and 2015, were due to dislocation.¹

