1. OBJECTIVES

Primary objective:

To investigate whether there is a difference in the number of hip dislocations following primary total hip arthroplasty (THA), using the posterolateral approach, with a dual-mobility (DM) cup compared to a unipolar cup in elderly patients 1 year after surgery.

Secondary:

- To investigate whether there is a difference in the number of revisions 1 year after surgery.
- To investigate what the cost-effectiveness and cost-utility of a DM cup is, compared to a unipolar cup after primary THA, from the health care and societal perspective at 1 year follow-up.
- To investigate whether there is a difference in the number of hip dislocations and revisions following primary THA with a DM cup compared to a unipolar cup 2 years after surgery.
- To investigate whether there is a difference in patient reported outcomes following primary THA with a DM cup compared to a unipolar cup 1 and 2 years after surgery.
- To compare long-term (5 and 10 year) implant survival based on revision and mortality data from national joint registries.
- To compare the number of hip dislocations, revisions and PROM data between patients in the randomized DM group and patients in an observational cohort DM group.

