3.4 Sample size calculation

Exact dislocation rates in the Netherlands are unknown. Based on previous studies and reviews, we assume that current dislocation rate for unipolar cups is 4% whereas DM cups result in 1% dislocation. $^{10;12;14;15;17;18;46}$ Power analysis indicates that a total sample of 976 (488 in each group) is needed to detect a difference in dislocations between 4% in the unipolar cup group and 1% in the dual-mobility cup group, using the chi-square test with 80% power and α =0.05. To account for loss to follow-up, 550 patients will be included in each group.

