5. METHODS

5.1 Study parameters/endpoints

5.1.1 Main study parameter/endpoint

The total number of dislocations, regardless of type of treatment (i.e. closed repositioning or revision).

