5.3 Study procedures

During the pre-operative visit at the outpatient clinic, patients who are potential candidates for this study will be screened to determine if they meet the inclusion / exclusion criteria. If the patient is eligible, the investigator (or his designated representative) informs the patient about the study and proposes study participation, according to GCP guidelines. If desired, an additional telephone appointment can be arranged. Patients must sign an ethical committee (METC) approved study informed consent form (ICF) prior to participating in any study specific activities. The ICF can be signed face to face by the patient and investigator, or the patient can sign the ICF remotely and send it to the investigator by mail (due to COVID-19 restrictions). Subsequently, the investigator can sign the ICF and send one version to the patient. The ICF will be stored in a locked closet in the participating center. Pre-operative data will be collected including: demographics and medical history, NRS for pain in rest and during weight bearing, HOOS-PS and EQ-5D. The patients are also asked to fill out questionnaires. See table 1 for an overview of all measurements and follow-up moments.

Evaluation moment	Pre-operative	Intra-operative	3 months	1 year	2 years
Preoperative data (screening)	х				
Surgical Details		х			
PROMs	х		х	х	х
Serious Adverse Events	Anytime				

Table 1: Overview of follow-up moments.

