6.2 AEs, SAEs and SUSARs

6.2.1 Adverse events (AEs)

Adverse events are defined as any undesirable experience occurring to a subject during the study, whether or not considered related to the implants. Only relevant adverse events reported spontaneously by the subject or observed by the investigator

or his staff will be recorded. The following AE's are directly related to the surgical procedure, and will therefore not be recorded by the investigator: nausea, headache, pain, haemorrhage and wound leakage

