6.2.2 Serious adverse events (SAEs)

A serious adverse event is any untoward medical occurrence or effect that

- results in death;
- is life threatening (at the time of the event);
- requires hospitalisation or prolongation of existing inpatients' hospitalisation;
- results in persistent or significant disability or incapacity;
- is a congenital anomaly or birth defect; or

(S)AEs that are related to a previous known or unknown disease, or conditions that cannot be related to the procedure (like accidents or related to other interventions) will not be recorded. An elective hospital admission will not be considered as a serious adverse event.

The investigator will report the potentially study-related SAEs, as defined above, through the web portal *ToetsingOnline* to the accredited METC that approved the protocol, within 7 days of first knowledge of the investigator for SAEs that result in death or are life threatening followed by a period of maximum of 8 days to complete the initial preliminary report. All other SAEs will be reported within a period of maximum 15 days after the investigator has first knowledge of the serious adverse events.

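### The protocol names no source or active collection for dislocations, its primary endpoint, and the only event recording it describes is selective

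*Protocol*

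**What the plan says.** **Endpoint.** Section 5.1.1 defines the primary endpoint as "The total number of dislocations, regardless of type of treatment (i.e. closed repositioning or revision"). Section 1 sets the comparison as a dual-mobility cup "compared to a unipolar cup in elderly patients 1 year after surgery"; dislocations at 2 years are a secondary objective.

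**Schedule.** Section 5.3 tells the reader: "See table 1 for an overview of all measurements and follow-up moments". The rows of Table 1 are preoperative data, surgical details, PROMs and serious adverse events (at any time). There is no row for dislocation and none for non-serious adverse events.

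**Questionnaires.** Section 5.1.2 lists function, quality of life, pain, change in functioning, fear of dislocation, costs connected with dislocation or surgery (3 months and 1 year only), education, and awareness of cup type. No item asks whether a dislocation happened.

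**Event recording.** Section 6.2.1 begins "Only relevant adverse events reported spontaneously by the subject or observed by the investigator" and extends this to the investigator's staff. Section 6.2.2 adds that "conditions that cannot be related to the procedure (like accidents or related to other interventions) will not be recorded". One of its seriousness criteria is an event that "requires hospitalisation or prolongation of existing inpatients' hospitalisation".

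**Other statements that bear on the source.** The Summary says that much of the information needed is already in the Dutch register. It describes the burden of participation as the "time needed to complete the cost questionnaires (all other outcomes are part of standard care"). Section 3.4 says "Exact dislocation rates in the Netherlands are unknown".

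**The concern.** A dislocation reduced in an emergency department without admission counts under 5.1.1. It may meet no seriousness criterion in 6.2.2, and Table 1 schedules serious events only. It can still be recorded as a non-serious adverse event, but only if someone judges it relevant and either the patient mentions it or staff see it. If it was treated at another hospital, staff may never see it. A dislocation after a fall also counts under 5.1.1, yet may be set aside under the accident wording of 6.2.2.

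The trial expects few events, so modest under-capture matters. Equal loss in both arms shrinks the absolute difference and the power while leaving the risk ratio unchanged. Unequal loss would bias the ratio as well. Section 5.2 states blinding for patients only, and whether an event is relevant or related to the procedure is a judgement that may be made by staff who know which cup was implanted.

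This is not a matter that an analysis plan can settle: events that were never collected cannot be recovered at analysis.

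**Working it through.** **1. Is there a stated route for each kind of dislocation?**

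| Kind of event | Counts under 5.1.1 | Route described in the protocol |
|---|---|---|
| Treated by revision | Yes | Possibly the register, which holds reasons for revision (Introduction) |
| Closed reduction with admission | Yes | SAE recording, subject to the relatedness exclusion |
| Closed reduction without admission | Yes | AE recording if relevant and volunteered or seen by staff; perhaps hinted at by the cost questions up to 1 year |
| After a fall | Yes | As above, but depends on how the accident wording is read |
| Between 1 and 2 years, no revision | Yes (secondary objective) | (S)AE recording only; the cost questions have stopped |

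None of these routes is named as the source of the endpoint.

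**2. Reproduce the planned sample size.** Inputs from section 3.4: 4% v 1%, α = 0.05 (taken as two-sided), power 80%, chi-square test.

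- Mean rate p̄ = (0.04 + 0.01)/2 = 0.025; difference 0.03.
- Without correction: n = [1.960·√(2·0.025·0.975) + 0.842·√(0.04·0.96 + 0.01·0.99)]² / 0.03² = 424 per arm.
- With continuity correction: n′ = (n/4)·[1 + √(1 + 4/(n·0.03))]² = 488.4 per arm.

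The stated 488 therefore reproduces with the continuity correction. The sample size is not at fault, but it presumes that every event is captured.

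**3. Expected events at 488 per arm.** Full capture: 488 × 0.04 = 19.5 and 488 × 0.01 = 4.9, about 24 in all. With 30% missed in each arm: 13.7 and 3.4, about 17.

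**4. Power under equal under-capture.** The missed share m is not in the documents; 0% to 50% is an assumed range. Each rate is multiplied by (1 − m), and the two binomial distributions are enumerated exactly at 488 per arm, two-sided 5%.

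| Missed share | Rates | Power, uncorrected chi-square | Power, continuity-corrected |
|---|---|---|---|
| 0% | 4.0% v 1.0% | 88% | 82% |
| 20% | 3.2% v 0.8% | 80% | 70% |
| 30% | 2.8% v 0.7% | 73% | 63% |
| 50% | 2.0% v 0.5% | 56% | 45% |

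**5. Do single events decide the result?** This depends on the test. With 5 v 14 events of 488, p = 0.037 uncorrected, 0.064 corrected and 0.061 by Fisher. With 5 v 13, the values are 0.057, 0.096 and 0.093. Losing one event crosses 0.05 only for the uncorrected test, so this example carries little weight.

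**The case against.** **AE recording is not named as the source.** A reader might infer that dislocations reach the database only through (S)AE recording. No sentence says so. Section 6.2 belongs to safety reporting, and section 7.4 tests dislocations at the interim while weighing revisions and SAEs separately and informally, which suggests distinct data. This stands. What remains is that no other source is named either.

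**The safety rules are wider than they look.** Section 6.2.1 also takes events that staff observe, defines adverse events irrespective of relation to the implant, and does not list dislocation among the events left unrecorded. The accident wording covers only conditions that cannot be related to the procedure. A displaced study prosthesis after a fall may well be judged related. A reader might infer that fall-related dislocations are excluded; the text makes them ambiguous, no more.

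**Other routes exist.** Register data can show revisions for dislocation, the cost questions run to the primary time point, and the Summary refers to standard care. This also stands in part, but none of these is a defined collection step for closed reductions. Nor does the section 3.4 remark on unknown Dutch rates prove the opposite: it supports a planning assumption and does not show what the register holds for enrolled patients.

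**The form or the monitoring plan may contain the item.** That is possible, and those documents are not at hand. However, the protocol presents Table 1 as covering all measurements, and the primary endpoint is absent from it.

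**The size is assumed.** Correct. With the uncorrected test, power is still about the planned 80% when 20% of events are missed equally.

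**Conclusion.** The point holds as a gap in ascertainment. Section 5.1.1 counts events that Table 1, section 5.1.2 and section 6.2, followed as written, can fail to collect, and these sections need to be reconciled. It should be fixed, but it does not show that the primary result would be invalid.

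The size cannot be derived from the documents. Under equal loss of 20% to 30%, power at 488 per arm falls from 88% to 80% or 73% (uncorrected), or from 82% to 70% or 63% (continuity-corrected). These figures rest on the protocol's assumed 4% and 1% and on an assumed missed share. Loss that differs by arm is possible, because only patients are stated to be blinded, but nothing in the documents shows that it would occur or in which direction.

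**What to change.** - Add one item to the questionnaires already sent at 3 months, 1 year and 2 years: whether the operated hip has dislocated since the last questionnaire, how often, and where it was treated.
- Have site staff confirm each positive answer from the medical record.
- Add a dislocation row to Table 1.
- State in 5.1.1 and 6.2 that every dislocation of the study hip is recorded as an endpoint, whatever its cause or treatment, outside the recording exclusions of section 6.2.

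The cost is a small amendment, one extra question per form, and a chart check of roughly 25 to 30 patients: at 550 per arm the protocol's rates give 550 × 0.04 + 550 × 0.01 = 27.5 patients with a dislocation by 1 year.

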Most dislocations occur during the first year after surgery, of which approximately half within the first three months after operation.²⁻⁵ Hip dislocation is a major problem that results in reduced functioning and a deterioration in quality of life⁶, especially in patients with recurrent dislocation who often need revision surgery. In order to establish value based health care for patients with hip osteoarthritis, hospitals within the Santeon network asked patients which outcomes are of value to them. The patients indicated that they feared hip dislocation and that its prevention is paramount to them [personal communication]. In addition to the negative consequences of dislocation for the patients, dislocations also increase healthcare costs.^{7;8} A single dislocation was estimated to add 19% to the hospital costs of an uncomplicated THA, and a revision surgery up to 148%.8 With an average cost for a primary THA of about €10.000 in the Netherlands, this implies additional costs after dislocation that range from €1.900 to €15.000 per case. To address the problem of dislocation, the dualmobility (DM) cup was developed in France in the 1970's. 10 The DM cup consists of two articulations between three different components; a metallic acetabular shell, a mobile polyethylene liner and a femoral head. The mobile polyethylene liner articulates both with the acetabular shell and the femoral head. This should provide more stability and biomechanically reduce the risk of dislocation. 11-14 Dislocation rates reported for the DM-cup range from 0 to 4.6%12;14-18 which seems slightly lower than the 0.5 to 6% reported for unipolar cups. 19-24 Also, the use of DM cups for revision surgery in patients with recurrent dislocation has shown promising results.^{2;25;26} The Dutch national arthroplasty registry (LROI) shows that in 2015 3.9% of all cemented cups was a DM cup.²⁷ These DM cups are mainly used in patients with specific characteristics, such as cognitive impairment (not able to follow restrictions after surgery) or neuromuscular diseases (spasms) or as a standard procedure for revision surgeries due to recurrent dislocations. Internationally, DM cups are used more widespread. For instance, in France DM cups are used in an estimated 30% of all THAs.²⁸ Potential disadvantages of DM cups are loosening, intra prosthetic dislocation and psoas impingement.^{29;30} In the Netherlands, most DM cups are placed because of specific patient characteristics.³¹ These characteristics might negatively affect the risk for dislocation and revision surgery compared to the general THA population. Nevertheless, several studies reported similar failure rates between DM and unipolar cups. 12;14;17;32

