7.2 Secondary study parameter(s)

Secondary study parameters concern revision surgery, and patient reported physical functioning, quality of life, pain, satisfaction, fear of hip dislocation, healthcare and societal costs, device-related complications and reoperations. The secondary outcomes will be analysed using similar multilevel models as appropriate for each outcome (linear/logistic/survival).

Cost-effectiveness analysis

An economic evaluation will be performed from the societal perspective, for dislocation and Quality Adjusted Life Years (QALYs). Prevailing guidelines of Zorginstituut Nederland will be observed. All costs and consequences relevant to THA, hip dislocation and hip revision will be taken into account.

To compare costs between groups, confidence intervals around the mean differences in costs at one year after THA will estimated using the bias-corrected and accelerated bootstrap method. To account for possible clustering of data and to adjust for possible confounders, multilevel analyses will be performed. To graphically present the incremental cost-effectiveness ratios and uncertainty around them, bootstrapped cost-effect pairs will be plotted on cost-effectiveness planes. Cost-effectiveness acceptability curves will present the probability that the dual-mobility cup is more cost-effective than the unipolar cup for a range of willingness-to-pay thresholds. To study the robustness of these results, sensitivity analyses will be performed.

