7.4 Interim analysis (if applicable)

Interim analyses for the primary study outcome will be performed when 200 patients have reached the 3 months postoperative PROM evaluation point. In the interim analyses the number of dislocations in each group will be compared. A chi-square test will be used and in case the assumptions of this test are not met, Fischer exact test will be applied. To guard against a type 1 error, we use the O'Brien-Fleming approach. As only one interim analysis will be performed, the alpha for this analysis is set at 0.005. Testing will be done two-sided. Furthermore, we will take the number of revisions and SAE's in each group in consideration, but will not formally test for differences in these. Results of the interim analysis will be discussed with the steering committee, Van Rens Foundation and the ethical committee. In case of a statically significant and relevant higher number of dislocations in the DM group, or more revisions or SAE's, appropriate actions will be taken (such as an early termination of the study).

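### Section 6.2.2 removes every elective admission from the SAE definition, so a planned re-admission for a complication of the operated hip can miss SAE reporting

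*Protocol*

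**What the plan says.** Under section 6.2.2 an occurrence is an SAE if, among other criteria, it "requires hospitalisation or prolongation of existing inpatients' hospitalisation" or "results in persistent or significant disability or incapacity". Exclusions follow. Events related to a previous disease are not recorded, and "conditions that cannot be related to the procedure (like accidents or related to other interventions) will not be recorded". The next sentence reads: "An elective hospital admission will not be considered as a serious adverse event". It carries no condition on when the admission was planned or what it is for.

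Reporting to the METC depends on that definition: "The investigator will report the potentially study-related SAEs, as defined above, through the web portal". The limit is 7 days for fatal or life-threatening events and 15 days for other SAEs.

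Other sections that bear on the point:
- 6.3 marks the annual safety report as not applicable, and 6.5 states that there will be no DSMB.
- 7.4 has one interim analysis, when 200 patients have reached 3 months. Besides dislocations, "we will take the number of revisions and SAE's in each group in consideration", without a formal test. More revisions or more SAEs may each lead to action, including early termination.
- 5.1.1 counts all dislocations however they are treated. 5.1.2 counts revision of any component for any reason. 7.2 adds "device-related complications and reoperations".
- 9.4 has an annual progress report to the METC that names SAEs and other problems, but not revisions.

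**The concern.** An exclusion for elective admissions normally serves to keep out admissions that were already arranged or have nothing to do with the trial treatment. Here unrelated conditions have been removed by the preceding sentence. The elective rule therefore acts mainly on planned admissions that can be related to the procedure, such as a scheduled re-admission for a problem with the operated hip.

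This matters because SAEs are the only safety events for which the protocol sets a continuous, time-limited route to the METC. The introduction states: "Potential disadvantages of DM cups are loosening, intra prosthetic dislocation and psoas impingement". Loosening and impingement are problems that can lead to a scheduled rather than an emergency admission. Two sites that follow the text could also classify the same re-admission differently, depending on whether they read the sentence as excluding the admission or the event behind it.

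**Working it through.** The point is textual, and no figure in the protocol is an input to it. The check sets the sections side by side and follows each type of event through the counts that the protocol defines.

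**Step 1: what the elective sentence acts on.** Start from the hospitalisation criterion. Remove events due to previous disease and conditions that cannot be related to the procedure (sentence before). What remains is mainly admissions related to the procedure. The elective sentence splits these into unplanned (SAE) and planned (not an SAE by this criterion).

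**Step 2: where each event is counted, on a literal reading.**

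| Event in the operated hip | SAE through hospitalisation (6.2.2) | Interim (7.4) | Study outcome |
|---|---|---|---|
| Unplanned admission for a complication | Yes | Yes, as SAE | According to type |
| Dislocation with planned re-admission | No | Yes, as dislocation | Primary (5.1.1) |
| Planned revision of a component | No | Yes, as revision | Secondary (5.1.2) |
| Planned reoperation without component exchange | No | Not listed | Named in 7.2 |

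The last row assumes that a reoperation which leaves all components in place is not a revision. Section 7.2 supports this by naming reoperations separately from revision surgery.

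**Step 3: what the METC receives.** The 7- and 15-day route carries only SAEs as defined in 6.2.2. There is no DSMB and no annual safety report. The ethical committee does see revisions and SAEs at the interim, but only once. By then 200 of the 1100 planned randomised patients (200 / 1100 = 18%) have reached 3 months of a 24-month follow-up. After that, the annual progress report is the remaining scheduled channel. It names SAEs, and planned revisions or reoperations could enter it only under other problems.

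**Step 4: can the loss be counted?** No. The protocol gives no rate of planned re-admission, of reoperation without exchange, or of the share of revisions that are elective. Section 4.1 gives 5-year survival above 95% for both cups. If that carries over to this trial, fewer than 0.05 × 1100 = 55 randomised patients would be revised in 5 years. That figure covers revisions, planned and unplanned, which are already counted elsewhere, and a longer period than the 2-year follow-up. It does not measure the gap.

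**The case against.** The strongest reply is that little is lost. Component revision is counted whether elective or not, is discussed with the ethical committee at the interim, and is a ground for action in its own right. Dislocations are the primary endpoint. Reoperations and device-related complications are named secondary parameters. All of this stands, and it limits the point to SAE reporting and to the interim list.

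A second reply is that the sentence excludes an admission, not the event behind it. Loosening could still be an SAE through the disability criterion, or be recorded as an AE. In the text at hand the list of criteria also ends on a conjunction, so a further criterion may have been lost. This stands in part. Some events would be caught that way, but not those whose only serious feature is the planned admission. The AE route is weaker: 6.2.1 records only relevant events that are volunteered or observed and leaves out pain, and the protocol states no METC route for AEs.

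Third, the METC has other information: the interim results, the yearly report of other problems, and notification of any suspension on safety grounds (6.1). This is correct, but none of these replaces case-by-case reporting within 15 days.

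Two stronger readings are tempting and not supported:
- A reader might infer that planned cup revisions disappear from the interim review, or that a formal interim comparison of SAEs is distorted. Revisions are counted separately there, and SAEs are not formally tested.
- A reader might infer that the rule makes the dual-mobility cup look safer. The introduction calls the listed disadvantages only potential, and it also reports that several studies found similar failure rates for the two cup types. No direction of bias follows.

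**Conclusion.** The point holds in a limited form. As written, 6.2.2 keeps planned re-admissions for complications of the operated hip out of the SAE definition as far as hospitalisation is concerned, and so out of the 15-day METC route and the SAE tally. Two gaps remain: ongoing SAE reporting to the METC, chiefly after the single early interim, and planned reoperations without component exchange, which are absent from the interim list although 7.2 analyses them.

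The size cannot be estimated from the documents. The sample size and the primary analysis are not affected, and revisions and dislocations are not lost as outcomes. The conclusion rests on a literal reading of the elective sentence and on no unseen SAE criterion covering these admissions. The sponsor may have meant only pre-planned or unrelated admissions, but the text does not say so.

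**What to change.** At the next amendment:
1. In 6.2.2, limit the exclusion to hospital admissions already planned before enrolment and to elective admissions for a condition unrelated to the operated hip.
2. In the same place, state that any admission for a complication, reoperation or revision of the operated hip, planned or unplanned, is reported as an SAE.
3. In 7.4, list reoperations next to revisions among the counts considered per group.

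The cost is a short change of text in two sections and a small number of extra SAE forms, some of them for patients whose revision is recorded anyway. No analysis or recruitment target changes.
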